10.4.3 Handling of missing values/censoring/discontinuations

Patients who are ineligible for the DDS may be replaced as described in Section 7.1.4.2. Continuing events (e.g. AEs, concomitant medication, etc) will be summarized using the data cut-off date as the date of completion, with an indication within listings that the event is continuing. For patients who discontinue the study with ongoing events, the discontinuation date will be used as the completion date of the event with the appropriate censoring as described in the above paragraph.

Patients for whom no best overall response can be assessed at the time of the primary analysis will be treated as treatment failures.

The reason for discontinuation from study will be summarized and listed, along with dates of first and last study drug treatment, duration of exposure to study drug treatment and date of discontinuation for each patient.

Other missing data will simply be noted as missing on appropriate tables/listings.

10.4.4 Supportive analyses

CCI

If deemed necessary, a sensitivity analysis will be performed using central imaging assessments according to RECIST v1.1 (see [Appendix 1, Section 14.1](#)). The same method of analysis as for the primary analysis will be used, using the FAS.

10.5 Secondary objectives

10.5.1 Efficacy

Phase Ib. A secondary objective of the Phase Ib is to assess preliminary clinical anti-tumor activity of the combination in patients with BRAF V600-dependent advanced solid tumors. For all efficacy analyses the FAS will be used.

Anti-tumor activity will be assessed using the Investigator imaging assessments under RECIST version 1.1, [Appendix 1](#). The Best Overall Response (BOR) for each patient and individual lesion measurements will be listed. The (BOR) is the best response recorded from the start of the treatment until disease progression. ORR will be estimated for this patient population. TTR and DOR will be assessed if at least one responder is observed.

Phase II. Local imaging assessments will be used for all Phase II efficacy assessments of tumor activity. The FAS will be used.

Overall survival (OS) is defined as the time from start of treatment to date of death due to any cause. If a patient is not known to have died, survival will be censored at the date of last contact. Kaplan-Meier estimates with confidence intervals for median survival and survival probabilities for specific time points will be presented.

The secondary endpoint progression-free survival (PFS) will be analyzed using Kaplan-Meier estimates (including plots) with 95% confidence interval for median survival. If a patient has not had an event, he/she will be censored at the date of last adequate response assessment. PFS is defined as the number of days from the first day of treatment to the date of the first documented progression of disease or date of death, whichever occurs first. PFS will be summarized by arm.

Kaplan-Meier estimates based on all responders with 95% confidence intervals will be presented for the secondary endpoint duration of overall response (DOR). This analysis based on responders will be used as a descriptive analysis. DOR is the time between the date of first documented response (CR or PR) and the date of documented progression or censoring. Censoring will occur at the last adequate tumor assessment date at which continued response is documented.

The secondary endpoint time to response (TTR) is the time between the date of first treatment administration and the first documented response (CR or PR). Patients who did not achieve a confirmed PR or CR will be censored at the last adequate tumor assessment date when they did not progress, or at maximum follow-up (i.e. FPFV to LPLV used for analysis) when they had an event for PFS.

If deemed necessary, analyses of TTR and DOR as described above, will be performed using central imaging assessments (RECIST v1.1). FAS will be applied.

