If more than one dose combination or dosing schedule has been defined as MTD/RP2D, the Sponsor may decide to open the Phase II arms for more than one MTD/RP2D and/or start the Phase II arms with different dose combinations or schedules. This decision will be driven by the data available and will be discussed and agreed on between the Sponsor and the investigators.

30-day safety follow-up assessments

After study drug discontinuation, all patients must complete End of Treatment assessments within 14 days and the safety follow-up assessments for 30 days after the last dose of the study treatment (see also [Section 7.1.4](#) and [Section 7.1.5.1](#)).

Study evaluation completion (SEC)

Note: As of protocol amendment 10, patients will be considered to have completed the study after the 30-day safety evaluation or 30 days after treatment discontinuation, whichever is earlier.

The study evaluation completion (SEC) eCRF page records the end of study for every individual patient. For details on the time point of completion of SEC, please refer to [Section 7.1.4](#).

Disease progression and Survival follow-up assessments (Phase II only)

Note: As of protocol amendment 10, post-treatment disease progression follow-up (if applicable) and/or survival follow-up (including documentation of subsequent antineoplastic therapies) will no longer be performed for any patient in the Phase II part of the study.

Patients enrolled in the Phase II part of the study who discontinue study treatment for any reason other than disease progression will be followed up for progression of disease as detailed in [Table 7-1](#) and [Section 7.1.5.2](#). All patients enrolled in the Phase II part of the study will be followed for survival (for details see [Section 7.1.5.3](#)).

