4.3 Definition of end of the study

Note: As of protocol amendment 10, the end of study will be when the last patient on treatment completes the 30-day follow-up visit or 30 days after treatment discontinuation.

End of study (Last Patient Last Visit [LPLV]) will be upon completion of the follow-up period for the last patient treated with either the dual (LGX818 and MEK162) or triple (LGX818 and MEK162 and LEE011) combination as described in Section 4.1. This will occur once the last patient in the Phase II part has died or all patients have completed SEC, or have been lost to follow-up or withdrew consent, whichever occurs first.

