7.1.5.3 Survival follow-up period

Note: As of protocol amendment 10, no survival or subsequent antineoplastic therapy information will be collected.

All patients enrolled in the Phase II part of the study will be followed for survival every 3 months per phone call until death, or until all patients have completed SEC, or have been lost to follow-up or withdrew consent, whichever occurs first. Possible newly started antineoplastic therapies during this FU period must be recorded on the Antineoplastic therapy since discontinuation eCRF.

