Additional data for any patients continuing to receive the LGX818 and MEK162 dual combination past the cut off point for the initial reporting, as allowed by the protocol, and the Phase Ib/II patients' data from the LGX818 and MEK162 and LEE011 triple combination will be summarized in a final CSR that will be prepared when all patients have completed or discontinued from the study.

The following rules will be followed for reporting results unless stated otherwise:

- **Phase Ib dose escalation data:** Cohorts of patients treated with the same dose combination and regimen during the dose escalation part will be pooled into a common treatment group. All summaries, listings, figures and analyses will be displayed / performed by treatment group unless otherwise specified.
- **Phase II data:** Data will be summarized and listed by study arm.

Screen failure patients are those who signed the informed consent, but never started the study treatment for any reason. For these patients, the eCRF data collected, [Section 7.1.2.2](#), will not be included in any analysis, but will be reported in the CSR as separate listings.

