- Date of last adequate tumor assessment is the date the last tumor assessment with overall lesion response of CR, PR or SD which was made before an event or a censoring reason occurred. In this case the last tumor evaluation date at that assessment is used. If no post-baseline assessments are available (before an event or a censoring reason occurred) the date of randomization/start of treatment is used.
- Date of next scheduled assessment is the date of the last adequate tumor assessment plus the protocol specified time interval for assessments. This date may be used if back-dating is considered when the event occurred beyond the acceptable time window for the next tumor assessment as per protocol (see [Section 14.1.26](#)).

Example (if protocol defined schedule of assessments is 3 months): tumor assessments at baseline - 3 months - 6 months - missing - missing - PD. Date of next scheduled assessment would then corresponds to 9 months.

- Date of discontinuation is the date of the EOT visit.
- Date of last contact is defined as the last date the patient was known to be alive. This corresponds to the latest date for either the visit date, lab sample date or tumor assessment date. If available, the last contact date from that survival follow-up page is used. If no survival follow-up is available, the date of discontinuation is used as last contact date.

In comparative studies with long follow-up period and therefore extended visit schedule, it may be useful to collect the survival status at a pre-specified cut-off within a limited timeframe for all patients with no documented death. In this case, this requires a contact to be made with the patient or with any reliable source of information on the patient’s status, but not requiring a specific visit to be scheduled

- Date of secondary anti-cancer therapy is defined as the start date of any additional (secondary) antineoplastic therapy or surgery.

If this is applicable for the study, it should be specified in the protocol if new cancer therapy is considered an event or endpoints are censored.

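### After Amendment 10 only patients still on drug add survival time, so late Kaplan-Meier estimates of overall survival are biased upward unless one common cut-off is set

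*Protocol*

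**What the plan says.** OS is a Phase II secondary endpoint (protocol Table 3-1). Section 10.5.1 calls for Kaplan-Meier estimates of the median and of survival at unnamed time points, with the censoring rule "If a patient is not known to have died, survival will be censored at the date of last contact".

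The follow-up behind this rule was a quarterly call for everyone: "All patients enrolled in the Phase II part of the study will be followed for survival every 3 months per phone call until death" (Section 7.1.5.3). The same section now opens with a note that ends it: "As of protocol amendment 10, no survival or subsequent antineoplastic therapy information will be collected".

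On-treatment patients are handled differently. They continue to have visits, and Section 4.1 says "patients will be considered to have completed the study after the 30-day safety evaluation or 30 days after treatment discontinuation, whichever is earlier". Section 4.3 ties the end of the study to them: "As of protocol amendment 10, the end of study will be when the last patient on treatment completes the 30-day follow-up visit".

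Appendix 1 (Section 14.1.25) defines last contact as the latest date the patient was known to be alive, taken from the survival page where there is one. Otherwise, "If no survival follow-up is available, the date of discontinuation is used as last contact date", and "Date of discontinuation is the date of the EOT visit".

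The introduction to Section 10 says that continuing dual-combination data and all triple-combination data "will be summarized in a final CSR that will be prepared when all patients have completed or discontinued from the study". The Amendment 10 list of changed sections includes nothing from Section 10.

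**The concern.** Censoring at last contact is harmless when loss of contact is unrelated to prognosis. From Amendment 10 the follow-up rule itself creates a relation.

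- Phase II patients who have stopped drug leave the OS risk set together at the amendment.
- Those still on drug stay in it, and each leaves on stopping drug or within 30 days. Under Section 4.1 treatment ends at progression, toxicity or withdrawal of consent, so departure usually comes just as the risk of death rises.

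After the amendment the curve is carried only by patients still on drug, who stand in for those who have stopped. Both selections push the estimate upward. At stake are late survival percentages and the apparent plateau. Arm A is the most exposed, because its Phase II results are planned for the final report only.

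**Working it through.** The protocol gives no OS event count, assumed survival or power, so there is no stated figure to reproduce. Counts below are from the Amendment 10 rationale and the arm size from Section 4.1. All hazards and calendar times are assumptions.

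**Step 1: who can add OS time.**

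| | On treatment | Off treatment, still followed | Total |
|---|---|---|---|
| Dual | 5 | 12 | 17 |
| Triple | 5 | 8 | 13 |
| All | 10 | 20 | 30 |

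The 20 are all Phase II. The Phase Ib/II split of the 10 is not given. After the amendment the 20 add nothing, and the Phase II patients among the 10 add time only until they stop drug. In arm A at most 13/40 = 32.5% of patients are involved.

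**Step 2: the residual triple-combination patients, 3 years on.** Yearly hazards: leaving treatment p, death on treatment m0, death after leaving m1, death in those already off treatment m2. Let t = 3 and g = 30/365.25 = 0.082 years.

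- S_on = exp(-(p+m0)t) + p/(p+m0-m1) × [exp(-m1·t) - exp(-(p+m0)t)]
- S_off = exp(-m2·t)
- True survival = (5·S_on + 8·S_off)/13
- Kaplan-Meier limit under the plan = exp(-[m0 + p(1 - exp(-m1·g))]·t)

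Middle case, p = 0.2, m0 = 0.02, m1 = m2 = 0.3:

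- S_on = 0.517 + (-2.5)(0.407 - 0.517) = 0.793 (unrounded inputs)
- S_off = 0.407
- True = (5 × 0.793 + 8 × 0.407)/13 = 0.555
- Plan = exp(-(0.02 + 0.2 × 0.0243) × 3) = 0.928

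Over p 0.1-0.4, m1 0.3-0.7 and m2 0.05-0.3, the plan gives 0.88-0.94 against a true 0.45-0.86. These values are conditional on being alive at the amendment. Multiplying by 13/40 gives a crude arm-level figure: 0.302 against 0.180 in the middle case (+12 points), with a range of +2 (0.304 against 0.280) to +14 (0.286 against 0.146). This scaling takes all five on-treatment patients as Phase II and gives everyone the same follow-up time.

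**Step 3: whole-arm simulation with staggered entry.** 40,000 patients per scenario enter over 1.5 years. The amendment falls 8 years after first entry (6.5-8 years for each patient) and the study ends at year 13. Long-term patients are 35%. The others leave treatment at 1.2 per year and then die at 1.0 per year.

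| Long-term p | m0 | Long-term m1 | Year 8: true / plan | Bias, points | Year 11: true / plan | Bias, points |
|---|---|---|---|---|---|---|
| 0.15 | 0.02 | 0.3 | 0.158 / 0.170 | +1.2 | 0.100 / 0.159 | +5.9 |
| 0.15 | 0.02 | 0.6 | 0.117 / 0.130 | +1.3 | 0.071 / 0.121 | +5.0 |
| 0.25 | 0.02 | 0.3 | 0.114 / 0.126 | +1.2 | 0.060 / 0.115 | +5.5 |
| 0.15 | 0.05 | 0.3 | 0.128 / 0.137 | +0.9 | 0.075 / 0.116 | +4.1 |
| 0.10 | 0.02 | 0.2 | 0.212 / 0.222 | +1.0 | 0.161 / 0.209 | +4.8 |

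At years 3 and 6, before the amendment for all patients at year 6 and earlier, plan and truth agree within 0.1 point.

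**Step 4: one common OS cut-off at the amendment.** The year 8 estimates become 0.155, 0.121, 0.116, 0.128 and 0.211, all within 0.5 points of the truth. Later times are then not estimable.

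**The case against.** Last-contact censoring is conventional, and an analysis plan that is not shown could set an OS cut-off or choose only early time points. The second part stands: Section 10.5.1 names no time points, and no harm is done if nothing beyond the amendment is presented. But the protocol itself fixes the censoring rule, the definition of last contact and reporting after all patients have stopped. Followed as written, these give the biased tail.

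The dual arms are less exposed. Their initial report is cut at last patient first visit plus 18 months, or earlier, when 80% can be assessed for PFS. They are affected only if OS is updated in the final report.

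Four stronger readings are tempting and are not supported.

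- That the plan reports about 93% survival where the truth is about 55%. This is conditional survival among 13 residual patients under assumed hazards, not an arm-level estimate.
- That OS is censored at progression. The rule is last contact, with the discontinuation visit as fallback; toxicity or withdrawal also ends treatment, and Section 6.1.5 allows some dosing beyond progression.
- That Phase Ib patients among the 10 make matters worse. Section 10.5.1 defines OS for Phase II only, and an arm with no Phase II patient on treatment has no such bias.
- That progression-free survival and duration of response suffer in the same way. On-treatment patients are observed up to progression, which is the event. Table 7-2 makes the scan interval institutional practice, so a scan on that schedule is not a missed one. The missed-assessment rule in Table 14-5 is only a default.

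**Conclusion.** The point holds for OS, and for late times only. As written, Kaplan-Meier OS beyond the amendment is biased upward, mainly in the tail of arm A and in any updated dual-arm OS. Medians and time points reached before the amendment are not affected.

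The best arm-level indication is about +1 point at year 8 and +4 to +6 points at year 11. The direction was the same in all five scenarios. The size rests on assumed hazards, on an assumed amendment date relative to entry, and on the unstated Phase II share of the 10 on-treatment patients.

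**What to change.** In Section 10.5.1, for OS only, set one administrative cut-off for all Phase II patients. It should be no later than the effective date of Amendment 10, and ideally the last complete 3-monthly survival sweep before it. Censor patients alive then at their last contact on or before that date. List later deaths without entering them in the Kaplan-Meier estimates.

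Do not apply the cut-off to progression-free survival or duration of response, where it would discard valid progressions and response time from the longest responders.

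The cost is one sentence and a date filter in programming. A few person-years and possibly one or two on-treatment deaths are listed rather than analysed, and OS cannot be estimated beyond the follow-up reached at the cut-off.

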14.1.21 Time to progression

Some studies might consider only death related to underlying cancer as an event which indicates progression. In this case the variable “Time to progression” might be used. TTP is defined as PFS except for death unrelated to underlying cancer.

Time to progression (TTP) is the time from date of randomization/start of treatment to the date of event defined as the first documented progression or death due to underlying cancer. If a patient has not had an event, time to progression is censored at the date of last adequate tumor assessment.

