14.1.23 Duration of response

The analysis following variables should be performed with much caution when restricted to responders since treatment bias could have been introduced. There have been reports where a treatment with a significantly higher response rate had a significantly shorter duration of response but where this probably primarily reflected selection bias which is explained as follows: It is postulated that there are two groups of patients: a good risk group and a poor risk group. Good risk patients tend to get into response readily (and relatively quickly) and tend to remain in response after they have a response. Poor risk patients tend to be difficult to induce a response, may have a longer time to respond, and tend to relapse quickly when they do respond. Potent agents induce a response in both good risk and poor risk patients. Less potent agents induce a response mainly in good risk patients only. This is described in more detail by (Morgan 1988).

It is recommended that an analysis of all patients (both responders and non-responders) be performed whether or not a responders only descriptive analysis is presented. An analysis of responders should only be performed to provide descriptive statistics and even then interpreted with caution by evaluating the results in the context of the observed response rates... If an inferential comparison between treatments is required this should only be performed on all patients (i.e. not restricting to “responders” only) using appropriate statistical methods such as the techniques described in (Ellis 2008). It should also be stated in the protocol if duration of response is to be calculated in addition for unconfirmed response.

For summary statistics on “responders” only the following definitions are appropriate. (Specific definitions for an all-patient analysis of these endpoints are not appropriate since the status of patients throughout the study is usually taken into account in the analysis).

Duration of overall response (CR or PR): For patients with a CR or PR (which may have to be confirmed the start date is the date of first documented response (CR or PR) and the end date and censoring is defined the same as that for time to progression.

The following two durations might be calculated in addition for a large Phase III study in which a reasonable number of responders is seen.

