G	Deaths due to reason other than deterioration of 'Study indication'	(1) Date of last adequate assessment	Censored (only TTP and duration of response)

1=Definitions can be found in [Section 14.1.25](#).
2=After the last adequate tumor assessment. "Date of next scheduled assessment" is defined in Section 14.1.25
3=The rare exception to this is if the patient dies no later than the time of the second scheduled assessment as defined in the protocol in which case this is a PFS event at the date of death.

The primary analysis and the sensitivity analyses must be specified in the protocol. Clearly define if and why options (1) are not used for situations C, E and (if applicable) F.

Situations C (C1 and C2): Progression or death after one or more missing assessments: The primary analysis is usually using options (1) for situations C1 and C2, i.e.

- (C1) taking the actual progression or death date, in the case of only one missing assessment.
- (C2) censoring at the date of the last adequate assessment, in the case of two or more consecutive missing assessments.

In the case of two or missing assessments (situation C2), option (3) may be considered jointly with option (1) in situation C1 as sensitivity analysis. A variant of this sensitivity analysis consists of backdating the date of event to the next scheduled assessment as proposed with option (2) in situations C1 and C2.

Situation E: Treatment discontinuation due to 'Disease progression' without documented progression: By default, option (1) is used for situation E as patients without documented PD should be followed for progression after discontinuation of treatment. However, option (2) may be used as sensitivity analysis. If progression is claimed based on clinical deterioration instead of tumor assessment by e.g. CT-scan, option (2) may be used for indications with high early progression rate or difficulties to assess the tumor due to clinical deterioration.

Situation F: New cancer therapy given: the handling of this situation must be specified in detail in the protocol. However, option (1), i.e. censoring at last adequate assessment may be used as a default in this case.

Additional suggestions for sensitivity analyses

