14.1.39 Censoring reason

In order to summarize the various reasons for censoring, the following categories will be calculated for each time to event variable based on the treatment completion page, the study evaluation completion page and the survival page.

For survival the following censoring reasons are possible:

- Alive
- Lost to follow-up
- For PFS and TTP (and therefore duration of responses) the following censoring reasons are possible:
 - Ongoing without event
 - Lost to follow-up
 - Withdrew consent
 - Adequate assessment no longer available*
 - Event documented after two or more missing tumor assessments (optional, see [Table 14-5](#))
 - Death due to reason other than underlying cancer (only used for TTP and duration of response)
 - New cancer therapy added (optional; only if the protocol specified that PFS/TTP will be censored at that date)

*Adequate assessment is defined in [Section 14.1.25](#). This reason is applicable when adequate evaluations are missing for a specified period prior to data cut-off (or prior to any other censoring reason) corresponding to the unavailability of two or more planned tumor assessments prior to the cut-off date. The following clarifications concerning this reason should also be noted:-

- This may be when there has been a definite decision to stop evaluation (e.g. reason=‘Administrative problems’ on study evaluation completion page), when patients are not followed for progression after treatment completion or when only UNK assessments are available just prior to data cut-off).

- The reason "Adequate assessment no longer available" also prevails in situations when another censoring reason (e.g. withdrawal of consent, loss to follow-up or alternative anti-cancer therapy) has occurred more than the specified period following the last adequate assessment.
- This reason will also be used for censor in case of no baseline assessment.

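### Section 10.5.1 and Appendix 1 of the protocol disagree on whether death due to the underlying cancer, without documented progression, ends duration of response.

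*Protocol*

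**What the plan says.** Protocol Section 10.5.1 defines DOR for responders: "DOR is the time between the date of first documented response (CR or PR) and the date of documented progression or censoring". The next sentence fixes the censoring date: "Censoring will occur at the last adequate tumor assessment date at which continued response is documented". Death is not mentioned. The same section defines the event for progression-free survival (PFS) as the "date of the first documented progression of disease or date of death, whichever occurs first".

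Appendix 1, Section 14.1.23, sets DOR by reference to another endpoint: "the end date and censoring is defined the same as that for time to progression". Section 14.1.21 gives that endpoint, TTP, an event of "the first documented progression or death due to underlying cancer". For deaths from other causes, situation G of Table 14-5 (Section 14.1.27) reads "Censored (only TTP and duration of response", and the list in Section 14.1.39 includes "Death due to reason other than underlying cancer (only used for TTP and duration of response". Table 14-5 also covers DOR in situation C2, where progression or death after two or more missing assessments is by default censored at the last adequate assessment.

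**The concern.** One protocol gives two end-point rules for one endpoint. A responder who dies of melanoma or colorectal cancer before a scan shows progression is censored as still responding under 10.5.1 and has an event under Appendix 1. Two programmers, each following the protocol, would report different event counts and different Kaplan-Meier curves.

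The 10.5.1 choice also has a direction. Death from the cancer says something about loss of response, so treating it as uninformative censoring favours a longer DOR. DOR is a Phase II secondary endpoint (Table 3-1), and Section 2.1 lists a more prolonged response among the questions for the triple combination against the dual. If the share of such deaths differed between the arms, the censoring rule would colour even an informal comparison.

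**Working it through.** The protocol states no DOR figure (no median, event count or power), so there is none to reproduce. The check is a comparison of the rules, followed by an illustration of size.

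**Step 1: what each rule does with a responder.**

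| First thing that happens | 10.5.1, DOR | Appendix 1, DOR | 10.5.1, PFS |
|---|---|---|---|
| Documented progression, at most one missed assessment | event | event | event |
| Cancer death, no documented progression, at most one missed assessment | censored at last scan in response | event at death | event |
| Cancer death after two or more missed assessments | censored | censored (default C2) | event as worded |
| Death from another cause | censored | censored (situation G) | event |

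The two DOR columns differ only in the second row. Patients who die after documented progression already have their event under both rules.

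**Step 2: direction.** Moving from Appendix 1 to 10.5.1 turns some events into censored times and creates none. The event count stays the same or falls, and from the date of death onward the Kaplan-Meier curve is the same or higher. Between the last scan and the death it can be marginally lower, because the patient leaves the risk set early. This offsets a little of the lengthening (Step 4).

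**Step 3: size under stated assumptions.** All inputs here are assumed. Let response end at a constant total hazard λ. Let q_c be the share of first ending events that are cancer deaths without documented progression (with fewer than two missed assessments), and q_o the share that are other deaths.

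- Event hazard under 10.5.1: λ(1 − q_c − q_o)
- Event hazard under Appendix 1: λ(1 − q_o)
- Event hazard for progression or any death: λ
- Median = ln 2 / event hazard
- Ratio of medians, 10.5.1 to Appendix 1: (1 − q_o)/(1 − q_c − q_o)
- Ratio of medians, 10.5.1 to progression or any death: 1/(1 − q_c − q_o)

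With a progression-or-any-death median of 8 months:

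| q_c | q_o | 10.5.1 median | Appendix 1 median | Ratio to Appendix 1 | Ratio to any-death rule |
|---|---|---|---|---|---|
| 5% | 0 | 8.42 | 8.00 | 1/0.95 = 1.053 | 1.053 |
| 10% | 0 | 8.89 | 8.00 | 1/0.90 = 1.111 | 1.111 |
| 20% | 0 | 10.00 | 8.00 | 1/0.80 = 1.250 | 1.250 |
| 5% | 5% | 8.89 | 8.42 | 0.95/0.90 = 1.056 | 1.111 |
| 10% | 5% | 9.41 | 8.42 | 0.95/0.85 = 1.118 | 1.176 |
| 20% | 5% | 10.67 | 8.42 | 0.95/0.75 = 1.267 | 1.333 |

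If q_c = 0, the ratio to Appendix 1 is 1, whatever q_o is.

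**Step 4: censoring at the last scan.** The formulas censor at the time of death, whereas 10.5.1 goes back to the last scan. A simulation with scans every 8 weeks, an 8-month median, q_o = 0 and no missed assessments gave 8.77 against 7.96 months at q_c = 10% (ratio 1.10), and 9.81 against 7.98 months at q_c = 20% (ratio 1.23). That is slightly less than the formula, in the same direction.

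**The case against.** The best defence has four parts.

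- **Appendix 1 is a generic guideline.** Its Table 14-5 options are defaults that the protocol or analysis plan may replace, and Section 14.1.29 expects study-specific choices there. That is right, but 10.5.1 is silent on death and does not say that it departs from Appendix 1. Elsewhere it relies on Appendix 1 for RECIST. An analysis plan may settle the matter, but it would have to choose between two rules that the protocol already states.
- **Such deaths may be rare.** Scans were scheduled every 8 weeks, or every 8 to 12 weeks after 24 months. Before Amendment 10, Phase II patients who stopped treatment without progression continued to be scanned. This stands: the share is unknown and could be near zero.
- **DOR carries little weight.** Section 10.5.1 calls the responder analysis descriptive, no decision rule or sample size uses DOR, and PFS and OS show the deaths. This stands and limits the importance of the point.
- **The overlap is large.** Appendix 1 itself censors non-cancer deaths for DOR and, by default, any death after two or more missed assessments. This also stands. A reader might infer that the two texts conflict on every responder who dies, or that Appendix 1 calls for progression or death from any cause as the DOR event. Neither is supported: Appendix 1 ties DOR to TTP, not to PFS.

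**Conclusion.** The point holds in a limited form. As written, 10.5.1 censors a responder who dies of the cancer without documented progression. Appendix 1 counts that death as an event, provided fewer than two assessments were missed. On non-cancer deaths the two texts agree.

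The effect runs towards a longer DOR. Its actual size cannot be derived from the protocol. The figures of about 5%, 11% and 25% rest on exponential hazards, no other deaths and assumed cancer-death shares of 5%, 10% and 20%; with no such deaths the difference is zero. It would be tempting to take 1/(1 − f), with f the share of all deaths without documented progression, as the size of the contradiction. That expression measures the gap to a progression-or-any-death rule and overstates the gap to Appendix 1 whenever other deaths occur.

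The primary ORR and DCR analyses are unaffected. The text should be corrected, but the trial's conclusions on response rate do not depend on it.

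**What to change.** State one DOR event definition in Section 10.5.1. It should count at least death due to the underlying cancer as an event, in line with Sections 14.1.21 and 14.1.23, and should say how deaths from other causes and deaths after two or more missed assessments are handled.

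Add a version that ends DOR at progression or death from any cause, matching the PFS event in the same section, as either the main or a sensitivity analysis. This version is a recommendation, since neither text now contains it for DOR. If it becomes the main definition, also change Section 14.1.23, situation G of Table 14-5 and the censoring-reason list in Section 14.1.39.

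The cost is a text edit: a sentence or two in 10.5.1 for the first option, and three further places in Appendix 1 for the second. Death dates are already collected for PFS and OS, so no new data are needed. Reported DOR may be slightly shorter.
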